### 2. STUDY AIMS AND OBJECTIVES

#### 2.1 Aims

- To assess the effectiveness of a short-term financial incentives-based intervention at bringing about behaviour change and improving ICS adherence and asthma control, in the short-medium term, in CYP with asthma.
- 2. To assess the feasibility of study processes, randomisation, and outcome assessments.
- 3. To generate pilot data that can be used to inform the power calculation and design of a definitive RCT of financial incentives in children with asthma.

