#### 2.2 Objectives

- 1. To recruit children and young people aged between 11-17 years with asthma and measure adherence using EMDs (programmed with reminders) and a self-report measure (MARS-A) during a 12-week intervention period when financial incentives are given and compare to a group given an EMD (programmed with reminders) only, and to continue to measure adherence during a subsequent 12-week period (when no financial incentives are given) to assess whether financial incentives lead to continued better adherence in the short-medium term compared to the control group.
- 2. To measure asthma outcomes (number of severe exacerbations, time to exacerbation, asthma symptoms and if feasible given COVID-19 constraints, exhaled nitric oxide) at baseline, 12-weeks, and 24-weeks to assess whether financial incentives lead to short-medium term changes in a range of asthma control measures compared to the control group.
- To measure habit (using the self-report behavioural automaticity index, SRBAI) and autonomous/controlled motivation (using a questionnaire adapted from the Treatment Self-Regulation Questionnaire (TSRQ)) at baseline, 12-weeks, and 24-weeks to

Research Governance and Integrity Team

assess whether financial incentives lead to short-medium term changes in medication taking habits and motivations compared to the control group.

- 4. To measure beliefs in medicine (using Beliefs in Medicines Questionnaire, BMQ) and perceptions of illness (using the Brief-Illness Perceptions Questionnaire, B-IPQ) at baseline, 12-weeks, and 24-weeks to assess whether financial incentives lead to short-medium term changes in beliefs and perceptions regarding medication and illness and compared to the control group.
- 5. To conduct focus groups with participants from both the intervention and the control group and interviews with parents/guardians using a topic guide to obtain feedback of the trial and inform the design of a larger RCT.

Research Governance and Integrity Team

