Fifty participants will be enrolled in the 24-week programme and will be randomly assigned to either the financial incentives-based intervention group or the control group using the online service Sealed Envelope™ which will allocate participants to each group on a 1:1

Research Governance and Integrity Team

basis. Participants will be told which group they have been randomly assigned to during study visit 1.

For all participants, there will be a total of 3 study visits: at baseline (0-weeks), at 12-weeks and at 24-weeks. All study visits will take place at the Children's Clinical Research Facility (CCRF) at St Mary's Hospital, Imperial College Healthcare NHS Trust. Due to the continued COVID-19 restrictions, remote study visits will be offered to participants through Microsoft Teams (joining link will be sent to parents electronically) and an option for study visits to be conducted (by the study coordinator) at participant's homes will also be available, if necessary. However, due to financial constraints, we would not be able to perform FENO remotely, so it will be removed as a secondary outcome measure in this event. All study visits will include the collection of asthma-related clinical data, questionnaire data and adherence data which will be described in detail below.

All CYP's GP's will be informed of the CYP's involvement in the study and a summary of results from each study visit will be sent to the CYP's GP. Information shared in this summary will include ACT score, FENO and adherence data. This summary will also be sent to parents. It is important to note that the study team will not be managing the CYP's asthma or intervening if their adherence is poor – this will be made clear to parents/guardians and CYP and it will be suggested they contact their GP or asthma nurse if there are any concerns throughout the study.

All CYP will be issued with an EMD (Hailie® sensor, Adherium, New Zealand) which attaches to their usual inhalers to electronically record inhaler actuation to provide % adherence data.

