#### **STUDY VISIT 1:**

Prior to any tests, it will be ensured that all parents/CYP understand all the information provided and have electronically signed the informed consent form.

Participants will be given the Hailie® sensor and shown how to use this, as described above. Participants will be assessed and given guidance on their inhaler technique and will be provided with an Asthma UK children's asthma plan (unless already in receipt of an asthma plan, see appendix for plan) which will be conducted by a clinical research nurse.

The following information will be collected from all CYP; demographics, asthma history, asthma adherence (measured by self-report, MARS-A), asthma control (measured by ACT questionnaire, FENO – which will be measured by the child breathing out slowly though a mouthpiece where the nitric oxide from the breath will be measured the sensor and computer) and behavioural/psychological data (measured by BMQ, B-IPQ, SRBAI, TSRQ-adapted for this study).

Participants will be randomly assigned to either the 1) control group (n=25) or to the 2) financial incentives-based intervention group (n=25). Participants will be told which group they have been randomly assigned to during this visit.

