#### 7.2 Statistical methods and sample size

As this is a pilot study, a formal sample size calculation is not required. However, the estimated sample size of 50 participants in total is based upon a calculation from unpublished adherence data obtained from Royal Brompton Hospital from 400 children. Mean adherence in the sample was 65% (SD 22%). A Cochrane review of adherence interventions to ICS for asthma found that electronic trackers or reminders led to better adherence of 19% (95% CI 14.47 to 25.26). Based upon this information, to give 80% power to achieve a 19% difference between the intervention group and controls, 21 participants are required per group. The target of 25 per group accounts for participant dropout. This is supported by evidence that as a pilot study, 25 participants per group, with a total of 50 participants is sufficient.

Data analysis will be conducted using the Statistical Package for the Social Services (SPSS). Statistical analysis of quantitative, normally distributed data will be reported with means ± standard deviations (SD) and non-parametric data will be reported as medians with interquartile range. Data will be tested for normality using visual inspection, histograms, and Kolmogorov-Smirnov testing. Parametric tests will be used where possible for normally distributed data and logarithmically transformed data, otherwise appropriate non-parametric tests shall be used. The significance levels for all tests will be set at <0.5.

Categorical data will be reported as proportions. Comparative analysis of variance between 2 groups for continuous data will be performed using the student's t test for normally distributed data and the Mann Whitney U tests for non-normally distributed data and for more than 2 groups the ANOVA or Kruskal Wallis respectively. A comparison of the proportions between groups will be performed using the Pearson Chi 2 tests. Within group analysis the ANOVA test will also be used.

Questionnaire data will be used alongside group comparisons to observe any notable changes or differences between groups.

Qualitative data obtained from the focus groups will be thematically analysed. An independent researcher will aid with the facilitation/analysis of qualitative aspect of the study to ensure there is no bias.

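### Section 7.2 does not say whether or how visit 1 values enter the comparison of secondary measures between arms, and names no method for censored time to exacerbation or for the listed incident rate ratio

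*Combined protocol and SAP*

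**What the plan says.** Section 7.2 is the only quantitative analysis text. For continuous data in two groups it names the "t test for normally distributed data and the Mann Whitney U tests for non-normally distributed data", and for proportions Pearson's chi-squared. It adds two sentences that might involve baseline: "Questionnaire data will be used alongside group comparisons to observe any notable changes or differences between groups" and "Within group analysis the ANOVA test will also be used". It mentions no baseline covariate, defined change score, survival method, censoring rule or rate model.

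The table in section 6 schedules ACT, FENO, MARS-A, SRBAI, BMQ, B-IPQ and the adapted TSRQ at 0, 12 and 24 weeks. It shows no EMD adherence value at visit 1. Objective 2 in section 2.2 measures asthma outcomes "at baseline, 12-weeks, and 24-weeks to assess whether financial incentives lead to short-medium term changes in a range of asthma control measures" relative to control, and objectives 3 and 4 are framed in the same way. FENO is conditional: for remote visits section 3 says "we would not be able to perform FENO remotely, so it will be removed as a secondary outcome measure in this event". Two motivation items in Appendix 1f go to the intervention group only.

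Section 3.1 lists time to next exacerbation treated with oral corticosteroids, and the total number of severe exacerbations with an incident rate ratio as its summary. Section 4.4 keeps data collected before a child withdraws, and section 7.2 expects losses: "The target of 25 per group accounts for participant dropout".

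**The concern.** There are two gaps.

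**(a) Baseline.** The objectives concern change relative to control, and baseline values are collected for seven measures. The between-arm tests named are unadjusted, and the plan does not say which quantity they are applied to. Within-group ANOVA does not estimate the difference between arms. Final values, change scores and baseline-adjusted values have different precision, and at 25 per arm that matters. An open choice can also be settled after the data have been seen.

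**(b) Exacerbations.** A child who is event-free at week 24, or who withdraws earlier, has a censored time. A t test or Mann-Whitney test needs a number for that child, and the plan gives no scoring rule. The rate ratio is named as a result, but no listed test produces one or allows for unequal follow-up.

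Section 2.1 makes these estimates part of the trial's purpose: "To generate pilot data that can be used to inform the power calculation and design of a definitive RCT". A definitive trial would be designed from the estimated differences and their intervals.

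**Working it through.** **Plan's own figure.** Section 7.2 gives SD 22, difference 19, 80% power and 21 per group. Taking two-sided 0.05 (the significance level is printed as below 0.5, a separate matter):

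n = 2 × (1.960 + 0.842)² × (22/19)² = 21.05 per group.

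This is an unadjusted comparison of the primary outcome. It agrees with the stated 21 apart from rounding up, and neither supports nor weakens the point. No figure is stated for any secondary outcome. The dropout allowance is 1 − 21/25 = 16%.

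**(a) Precision of the secondary comparisons.** From the plan: 25 per arm. Assumed: effect 0.6 SD, two-sided 0.05, equal SDs at each visit, and baseline correlation r = 0.3, 0.5 or 0.7, because the documents give none.

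- Standard error in SD units, final values: √(2/25) = 0.283.
- ANCOVA multiplies this by √(1 − r²); change scores multiply it by √(2(1 − r)).
- Noncentrality = 0.6 ÷ standard error. For final values it is 0.6/0.283 = 2.12; for ANCOVA at r = 0.5 it is 2.12/0.866 = 2.45.
- Power is from the noncentral t with 48 df (47 for ANCOVA). Half-width = t(0.975) × standard error.

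| r | Power, final | Power, change | Power, ANCOVA | Half-width, final | Half-width, change | Half-width, ANCOVA |
|---|---|---|---|---|---|---|
| 0.3 | 55% | 42% | 59% | 0.57 SD | 0.67 SD | 0.54 SD |
| 0.5 | 55% | 55% | 67% | 0.57 SD | 0.57 SD | 0.49 SD |
| 0.7 | 55% | 77% | 83% | 0.57 SD | 0.44 SD | 0.41 SD |

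ANCOVA does better than either reading of 7.2 at each r. At 0.8 SD the same formulas give 79% on final values against 83/89/97% with ANCOVA.

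**(b) Methods for the exacerbation outcomes.** Set against section 3.1, the tests in 7.2 (t, Mann-Whitney, ANOVA, Kruskal-Wallis, chi-squared) include none that accepts a censored time and none that returns a rate ratio. This part needs no arithmetic.

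Precision of a rate ratio, assuming Poisson counts, 24 weeks' follow-up for all 25 per arm and a true ratio of 0.5:

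- Control risk 50%: expected events −25 × ln(0.5) = 17.3 against 8.7. SE of log ratio = √(1/17.3 + 1/8.7) = 0.416. Interval 0.5 × exp(±1.96 × 0.416) = 0.22 to 1.13.
- Control risk 30%: expected events −25 × ln(0.7) = 8.9 against 4.5. SE = 0.580. Interval 0.16 to 1.56.

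Dropout or overdispersion would widen both.

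Time to exacerbation is equally limited. For HR 0.5, 80% power needs 4 × (1.960 + 0.842)²/(ln 0.5)² = 65.3, so 66 events. With 20–50% of 50 children having an event there would be 10–25.

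**The case against.** **The plan may intend to use baseline.** Sections 2.2 and 7.2 both speak of changes, and a t test on change scores would use baseline. A reader might infer that the plan ignores baseline altogether; the text does not support that. What stands is that the use of baseline is unspecified, and change scores are less precise than ANCOVA at each correlation tried.

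**Part (a) is about efficiency in a pilot.** The unadjusted tests are valid, and randomisation means no bias in expectation. Most of the measures are questionnaires, and the wording on them can be read as descriptive. At r = 0.3 the gain is small: 55% to 59%. All of this is fair and limits the weight of (a). It does not remove it, because the estimate and its interval feed the next trial's design even when no test is made.

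**Part (b) may seem to imply inflated false positives.** Simulation with 30–50% event risk does give 9–12% false positives with dropout of 24% v 8%, and 14–23% with 30% v 5%. That requires Mann-Whitney on time to exacerbation, event-free withdrawn children scored at their withdrawal time, and unequal dropout, all together. The plan states none of these. Unequal dropout is conceivable, because "Participants will be told which group they have been randomly assigned to during this visit" and only one arm is paid, but nothing in the documents predicts it. With equal 16% dropout the rate is about 5% under every scoring rule tried. With no dropout Mann-Whitney power (20–64%) is close to log-rank (21–66%) over the cases tried. The simulation illustrates one unstated rule and is not the size of the problem. The omission stands without it.

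**Conclusion.** Both parts hold as gaps in specification and are worth correcting before analysis.

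For (a), section 7.2 leaves the role of baseline open. In the cases tried, ANCOVA raises power from 55% on final values to 59/67/83% and narrows the 95% CI half-width from 0.57 SD to 0.54/0.49/0.41 SD. The gain depends on the assumed correlations; the power figures depend also on the assumed 0.6 SD effect. It applies to ACT, MARS-A, SRBAI, BMQ, B-IPQ, the motivation items common to both arms, and FENO where measured. It does not apply to the primary outcome, the proportion reaching 80% adherence, or the intervention-only motivation items. Adjustment corrects for chance imbalance only in the measured baseline and only through its linear effect. It also assumes that baseline answers are given before the child learns the allocation. The Study Visit 1 text describes collection first but does not make the order a rule.

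For (b), two listed outcomes have no suitable named method. This needs no assumption about dropout. Naming methods will not make these outcomes decisive: the expected interval for a true rate ratio of 0.5 includes 1 at either control risk.

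**What to change.** Leave the primary analysis as it is and add to section 7.2:

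- *(a) Each secondary measure with a baseline value in both arms is compared at 12 and at 24 weeks by ANCOVA on arm and baseline, reporting the adjusted difference with 95% CI. FENO is log-transformed by prior decision and reported as an adjusted ratio. Children without a baseline FENO are kept, using a missing-indicator or mean-imputed baseline. These comparisons are exploratory.*
- *(b) Time to next exacerbation is analysed from randomisation by Kaplan-Meier and log-rank, with a Cox hazard ratio and 95% CI, censored at last contact or week 24. Severe exacerbations are reported as a rate ratio with 95% CI from Poisson regression with a follow-up-time offset and robust standard errors.*

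Fixing the FENO transformation in advance avoids a data-dependent choice and makes clear that the result is a ratio. The exploratory label is needed because seven measures at two times already make 14 comparisons, before any subscales.

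The cost is a little more analysis work and one degree of freedom per covariate, with no extra participants or visits. Part (b) needs exacerbation dates, which the listed outcome already implies; asthma history is taken at every visit. Log-rank and Cox still assume that dropout is unrelated to exacerbation risk.

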### 8. REGULATORY ISSUES

#### 8.1. ETHICS APPROVAL

The Study Coordination Centre has obtained approval from the London-Bloomsbury Research Ethics Committee (REC) and Health Research Authority (HRA). The study must also receive confirmation of capacity and capability from each participating NHS Trust before accepting participants into the study or any research activity is carried out. The study will be conducted in accordance with the recommendations for physicians involved in research on human subjects adopted by the 18th World Medical Assembly, Helsinki 1964, and later revisions.

For participants involved in the financial incentives-based intervention, the financial incentives are gain-framed so participants will be rewarded dependent upon adherence behaviour, the reward will not be removed.

The clinical tests (FENO) may be familiar to participants. It is often used as routine care in many clinics. The test is very basic and will be fully described to the child.

The behavioural/psychological questionnaires (including SRBAI, BMQ, B-IPQ and adapted TSRQ), the self-report adherence questionnaire (MARS-A) and the focus group discussion will involve simple questions that should not be distressing.

Participants can refuse to answer any questions at any point.

All questionnaires are included in the appendix.

#### 8.2. CONSENT

Consent to enter the study must be sought from both parent/guardian and assent obtained from the CYP. Consent/assent must be sought only after a full explanation has been given, an information leaflet offered and time allowed for consideration. Signed participant consent/assent should be obtained. The right of the participant to refuse to participate without giving reasons must be respected. All participants are free to withdraw at any time from the protocol treatment without giving reasons and without prejudicing further treatment.

Consent will also be obtained separately from parents/guardians who will be taking part in the interviews.

#### 8.3. CONFIDENTIALITY

The Chief Investigator will preserve the confidentiality of participants taking part in the study and is registered under the Data Protection Act.

Data will be pseudonymised.

#### 8.4. INDEMNITY

Imperial College London holds negligent harm and non-negligent harm insurance policies which apply to this study.

#### 8.5. SPONSOR

Imperial College London will act as the main Sponsor for this study. Delegated responsibilities will be assigned to the NHS trusts taking part in this study.

#### 8.6. FUNDING

Imperial College London and AUKCAR are funding this study.

Finances:

- Awaiting quote from Adherium, New Zealand (regarding the Hailie sensors)
- Up to £168/participant (n=25) in financial incentives-based intervention group = £4,200
- Reimbursement costs for travel and for refreshments will be provided to parents/guardians/CYP who attend any study visits in person at the CCRF, St Mary's Hospital.

#### 8.7. AUDITS

The study may be subject to audit by Imperial College London under their remit as sponsor and other regulatory bodies to ensure adherence to GCP and the UK Policy Frame Work for Health and Social Care Research.

#### 9. STUDY MANAGEMENT

The day-to-day management of the study will be co-ordinated through [name] (CCRF, St Mary's Hospital, Imperial College London Healthcare Trust).

### **10. PUBLICATION POLICY**

The results of this study will be presented at national and international scientific meetings to audiences of both paediatric and adult respiratory, allergy and general physicians. All results will be submitted for publication in peer-reviewed medical journals using open access policies where applicable. We will also use appropriate patient facing social media and channels via Imperial College Public Relations team and AUKCAR communications team to disseminate results. Results will also be included in a submitted PhD thesis submission to Imperial College London and will be detailed on the AUKCAR website/newsletters.

### **APPENDIX:**

- 1. Questionnaires to be used in this study
  - a. Asthma Control Test (ACT)
  - b. Brief Illness Perceptions Questionnaire (B-IPQ)
  - c. Belief in Medicines Questionnaire (BMQ)
  - d. Self-Report Behavioural Automaticity Index (SRBAI)
  - e. Medication Adherence Report Scale for Asthma (MARS-A)
  - f. Autonomous/Controlled Motivation questionnaire (Adapted from the Treatment Self-Regulation Questionnaire for the purpose of this study)
- 2. Asthma UK Children's asthma plan

#### 1. Questionnaires to be used in this study

#### a. Asthma control test (ACT)

1. In the past	4 weeks, how much of the	time did your asthma keep	you from getting as much	done at work, school or he	ome?
All of the time	Most of the time	Some of the time	A little of the time	None of the time	SCORE
2. During the	past 4 weeks, how often ha	we you had shortness of b	reath?		
More than once a	Once a day	3 to 6 times a week	Once or twice a week	Not at all	SCORE
day					
	past 4 weeks , how often di p at night or earlier than u		wheezing, coughing, short	ness of breath, chest tightn	ess or pain)
4 or more nights a week	2 or 3 nights a week	Once a week	Once or twice in the past 4 weeks	Not at all	SCORE
4. During the	past 4 weeks , how often di	d you have to use your res	cue (blue) inhaler or nebu	liser medication?	
3 or more times a	1 or 2 times a day	2 or 3 times per week	Once a week or less	Not at all	SCORE
dav					
5. How would	you rate your asthma con	trol over the past 4 weeks?	,	·	
Not controlled at all	Poorly controlled	Somewhat controlled	Well controlled	Completely controlled	SCORE
				TOTAL SCORE	
				Completed by (circle): child / parent / both	1

Research Governance and Integrity Team

637

#### b. Brief Illness Perceptions Questionnaire (B-IPQ)

E. Broadbent et al. / Journal of Psychosomatic Research 60 (2006) 631-637

#### Appendix A. The Brief Illness Perception Questionnaire

For the following questions, please circle the number that best corresponds to your views:

How much does your illn	ess affect	your life								
0 no affect at all	1	2	3	4	5	6	7	8	9	10 severely affects my life
How long do you think y	our illness	will con	tinue?							
0 a very short time	1	2	3	4	5	6	7	8	9	10 forever
How much control do you	u feel you	have ov	er your i	llness?						
0 absolutely no control	1	2	3	4	5	6	7	8	9	10 extreme amou of control
low much do you think										
0 not at all	1	2	3	4	5	6	7	8	9	10 extremely helpful
Iow much do you experi	ence symp	toms fro	m your i	illness?						
0 no symptoms at all	1	2	3	4	5	6	7	8	9	10 many severe symptoms
low concerned are you a	bout your	illness?								
0 not at all concerned	1	2	3	4	5	6	7	8	9	10 extremely concerned
How well do you feel you	u understa	nd your i	illness?							
0 don't understand at all	1	2	3	4	5	6	7	8	9	10 understand very clearly
How much does your illn	ess affect	you emo	tionally?	(e.g. do	es it mal	ke you a	ngry, sca	red, upse	t or depr	essed?)
0 not at all affected emotionally	1	2	3	4	5	6	7	8	9	10 extremely affected emotionally

2.\_\_\_\_\_

